### **Postpartum anthropometric and other Clinical Data Collection: Adiposity and Body Composition Measurements.**

**Newborn; Infant anthropometric measurements.** Length obtained on a hard-surface infant measuring board, weight, head circumference and skin fold thickness measurements will be performed by a trained research team member at approximately 24 hours to 1 week of life. Length, weight, and skinfold thickness will also be performed by a trained research team member at approximately 48-56 weeks of life. An in-person training will be conducted for the infant skinfold, head circumference, and length measurements to standardize procedures across sites

We will use the PEA POD system to measure fat mass. It will be performed by a research team member at approximately 24- hours to one week of life. Briefly, the PEA POD Air Displacement Plethysmography System is calibrated by menu-operated system. A wig-cap is placed on the baby, and the baby is measured nude, first weighed, and then placed in the transparent test chamber for 2 minutes for volume measurements. The system accommodates all infant behaviors. Body volume and mass are utilized to calculate body density, and predictive equations are then used to determine body composition, including fat mass.

**Collection of Infant Stool sample: Microbiome.** A separate, optional consent will be presented by MOMFIT staff after the birth of the baby. A small sample of stool will be collected initially at the hospital and later by moms prior to clinic visits at 6 weeks and 12 months post-partum.

**Postpartum Women.** The BOD POD will be used to measure adiposity 6 weeks and 12 months post-partum. A body-clinging bathing suit and cap are worn. Two measures are taken (total time <15 min) by trained personnel using specified procedures and averaged to get the % body fat outcome measure. At 6 weeks and 12 months postpartum, waist and hip circumferences will be measured (in cm), using standardized methods.

**Infant; 12 month old.** The 12 month study visit will also be performed by a trained research team member at 48-56 weeks of life. Length will be measured on a hard-surface measuring board and weight will be measured on a calibrated scale. Length, weight and skinfold thickness will also be performed by a trained research team member at approximately 48-56 weeks of life. An in-person training will be conducted for the infant skinfold, head circumference, and length measurements to standardize procedures across sites

### ***4.5 Patient Management and Follow-up***

The Study Coordinator will continually be in touch with all participants in both groups. Scheduling of data collection visits will be an ongoing process with reminder calls/texts prior to each scheduled visit.

Participants in the Lifestyle Change group will further be followed by the nutritionist who will interact in person during individual and group sessions. In addition the Study coaches will be in touch weekly through electronic self-monitoring with feedback dialogue.

#### ***4.5.1 Retention Strategies***

Consent to be contacted throughout the study and beyond will be collected from all mothers in both groups. We anticipate the possibility of continued follow-up upon completion of this important study. Our experience in previous clinical trials with over 90% retention has demonstrated that building personal relationships with participants, regardless of group assignment, is the single most important factor in enhancing retention. We plan to assure that every participant feels special by treating her with friendliness and genuine interest. Our clinic staff is well versed in this approach. Use of Internet access has been successfully employed in other studies. We will establish a MOMFIT website and have password protected access for both groups. Web-Watcher ( Enhanced Usual Care) participants will have access to PDFs on childcare related topics that will be drawn from publicly available sources. Birthday and holiday cards will be provided for both groups as well as a study newsletter available online.. Each week participants in the Lifestyle Change group will be contacted with a “how is it going?” message. At the time of delivery, a baby gift card will be personally delivered to all new mothers in both groups with well wishes, the opportunity to meet the new baby and provide ongoing encouragement.

#### ***4.5.2 Strategies to Promote Adherence***

Electronic self-monitoring is the primary strategy for promoting adherence to weight management behaviors (i.e., self-monitoring diet, physical activity, weight). An online weight management program that provides online tools to self-monitor diet, physical activity and weight will be adapted for use. Individualized goals for dietary intake (calories, fat), and physical activity will be established at the outset of the intervention. Goals for self-monitoring of diet and activity behaviors will also be established. Dietary self-monitoring adherence will be defined as recording 2/3 meals per day on 5/7 days per week. Physical activity self-monitoring adherence will be defined as recording minutes of moderate-vigorous intensity activity on 5/7 days per week. Progress toward goals will be reviewed with participants on a weekly basis. Behavioral coaches will provide ongoing surveillance of self-monitoring behaviors (diet and physical activity), and will provide coaching as needed. Participants will be encouraged to weigh themselves daily or at least weekly. Weight will be coach-monitored at each intervention visit to provide ongoing surveillance. Communication about adherence will occur in person during study related clinic visits, by telephone, or by email. Goals will be reviewed with participants using a motivational interviewing framework to support and encourage autonomy and intrinsic motivation for healthy changes in diet and activity behaviors.

#### ***4.6 Safety Monitoring / Adverse Event Reporting***

Per the RFA, we propose to review all outcome data for monitoring adverse outcomes. We will collaborate with the central Data and Safety Monitoring Board (DSMB) on all aspects of data review. We will also name an obstetrician not connected with the study as the Safety Officer to review adverse events within one week of their occurrence for any link to the study protocol.

The following findings would generate a safety alert and specific action if noted during any study visit:

1. Weight loss from enrollment weight during pregnancy
  - Alert values will be weight loss of 4% or greater of enrollment weight for women who were overweight at enrollment and loss of 6% or greater of enrollment weight for women who were obese at enrollment.

- For the first weight loss alert, the research staff will notify the patient, discuss her energy balance activities, provide weight management counseling, and modify the intervention if appropriate. Participants with a first alert for weight loss will return for a repeat weight within 2 weeks. Repeat weights should be collected at the same location at which the original safety alert weight was collected.
- If the weight loss is the same or greater upon reassessment, the patient's prenatal care provider should be contacted by research staff and additional modifications to the intervention may be indicated (i.e. decrease exercise, increase caloric intake). If the weight upon reassessment is no longer at alert values, the participant will continue current study activity.

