##### 4.4.1 Intervention

###### **Control Group Description:**

The Control Group in this study is an enhanced Usual Care group. For purposes of potentially improving recruitment, this is called the Web-Watcher group, since the Usual Care involvement will primarily be based on clinical visits and referral to the MOMFIT website that is password protected . The Usual Care group will attend the baseline and all data collection visits (**Table 3**) conducted by trained research staff blinded to the group assignments. They will be informed of their group assignment at the Randomization Visit and for retention purposes will be offered 1 web-based intervention consisting of publically available websites that will be conveniently organized and targeted to pregnant women as listed in Table 1. This approach will help encourage and maintain involvement of these participants in the study but differentiate the potential influence of the study intervention versus the usual care provided by their OB or other clinical provider.

The interventions planned in both groups are presented in Table 1 as follows:

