- 3) PA = 1.27 if PAL is 60 min/day or more

During the Individual Visits, each participant will have her own energy needs calculated and her daily dietary calorie goals will be reviewed as indicated in **Table 2**. For weight control purposes in these overweight/obese women, MOMFIT will minimize increases in energy intake. This intentional energy deficit is calculated to enhance energy balance without compromising nutrient density. In order to reduce weight gain but achieve nutrient adequacy, we will recommend 75% and 50% of the calorie goals for overweight and obese participants, respectively as presented in Table 2. Careful monitoring for safety and prevention of weight loss during pregnancy will occur via weekly contacts. Weight gain or loss of 1 pound or more within one week will be further reviewed with the mother.

**Table 2. Calorie needs during pregnancy and lactation for nonobese women compared with recommendations to accompany reduced weight gain goal for overweight/obese MOMFIT participants**

Trimester or phase	Pregnancy and Lactation	IOM Addition Normal Weight	MOMFIT Addition Overweight	MOMFIT Addition Obese
IOM Weight Gain Goals (lbs) *		25-35	15-25	11-20
1 st trimester	Prenatal (kcal)	0	0	0
2 nd trimester	Prenatal (kcal)	340	255	170
3 rd trimester	Prenatal (kcal)	452	339	226
1 st 6 mos.	Breast milk only, no formula (kcal)	330	248	165
1 st 6 mos.	At least half breast milk, plus some formula (kcal)	70	53	35
1 st 6 mos.	Some breast milk, mostly formula (kcal)	0	0	0
2 nd 6 mos.	Breast milk only, no formula (kcal)	400	300	200
2 nd 6 mos.	At least half breast milk, plus some formula (kcal)	200	150	100
2 nd 6 mos.	Some breast milk, mostly formula (kcal)	0	0	0

\*

reference [3]

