(diffusion editing) and the low molecular weight components (Carr-Purcell-Meiboom-Gill pulse sequence) respectively. Ultra-performance liquid chromatography (UPLC)-MS profiling will be used in general screening mode using in-house methods [50]. Targeted analysis will be conducted for alkylresorcinols (fibre), prolinebetaine (citrus fruit) and S-methyl-L-cysteine sulphoxide (cruciferous vegetables) using a combination of UPLC-MS and NMR methods. Data will be analyzed using multivariate statistical tools including linear projection methods and cluster analyses in order to identify candidate metabolic biomarkers associated with obesity or intervention. Candidate metabolic biomarkers of obesity in pregnant mothers at baseline and 36 weeks will be identified using available databases, by further analytical experiments such as 2-dimensional NMR pulse sequences including homo and heteronuclear correlation spectroscopy, LC-NMR-MS etc and by statistical correlation spectroscopy methods [48]. Several mathematical strategies will be applied to achieve higher sensitivity in detecting panels of inter-related biomarker candidates associated with maternal weight gain, maternal BMI and infant birthweight and adiposity. These methods will accommodate the specific challenges posed by spectral data including low sample:variable ratio, colinearity of predictor variables, confounding factors or co-morbidities correlated with both predictor and outcome variables etc. A flexible framework based on generalized linear models will be implemented to identify univariate and multivariate relationships of predictor variables with outcomes while statistically accounting for potential confounding effects observed in human studies. The choice of a model will be considered based on the probability distribution of a clinical outcome and both Bayesian and conventional maximum likelihood inferences will be made.

In addition to the ASA24 nutrient data, diet quality differences will be measured by metabolomic assays specifically related to fruit/vegetable and dietary fiber intake as alkylresorcinols (fiber), prolinebetaine (citrus fruit) and S-methyl-L-cysteine sulphoxide (cruciferous vegetables) in maternal urine and cord blood.

**Weight** will be measured without shoes, wearing light clothing on a calibrated beam balance scale at the Baseline visit, and at 24-28 week, and 35-37 weeks prenatal visits and the 6 week and 12 month postpartum visits.

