#### **4.6.1 Potential Risks**

The risks of phlebotomy include pain, a bruise at the point where the blood is taken, redness and swelling of the vein and infection. Risks from the questionnaires include discomfort and emotional upset. There could also be some minor pain or discomfort from a pinch from the calipers used for assessment of body fat.

The limitation of caloric intake and gestational weight gain has the potential to lead to weight loss during the pregnancy. The effects of weight loss in this population are unknown, but could increase the risk of fetal growth restrictions. Patients who loose in excess of 5% of their weight at the Baseline visit will have their diet reassessed to reassure adequate caloric intake.

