### ***5.3 Interim Monitoring Plan***

The DSMB for the Consortium will have overall responsibility for monitoring the emerging results. For this and other trials conducted by the Consortium members, the focus of the DSMB will be on safety issues, recruitment, retention, protocol adherence and data quality and timeliness. The DSMB will meet at least twice each year and more frequently if needed.

Since the enrollment period is relatively short and planned analyses will be conducted by the Consortium, using outcome data from all of the centers, no interim monitoring for efficacy will be undertaken. Thus no group sequential stopping rules are specified. Any explicit stopping rules for harm will be determined by the DSMB. In addition, futility as defined by low conditional power to show a benefit given the outcome data to date will not be assessed. However, recruitment will be monitored by the DSMB and the recommendations of the group will be sought if accrual is falling below the goal needed to complete the project by the conclusion of funding.

For each meeting, a formal detailed statistical report will address all aspects of the trial, including baseline variables, outcome variables, compliance with the protocol, data quality, loss to follow-up (primary outcome missing), and protocol violations (such as randomization of ineligible patients). Outcomes will be reported in a cohort of patients randomized before a given date. All adverse events reported to date will be included, with an indicator showing new events since the previous meeting. Adverse events may be reported to some or all of the DSMB members on a more frequent basis if applicable, as requested by the DSMB.

Only outcome variables primarily assessed for safety reasons will be reported by treatment group, including inadequate weight gain for mother and infant. The DSMB will not be masked to group, unless specifically requested.

The DSMB will also consider new information from external sources such as the results of other randomized trials and results of meta-analyses of similar interventions. If this new information is judged relevant to all patients, the DSMB may recommend changes to the protocol or to the consent form.

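### Weight loss and participant-reported adverse events can be detected more often in the intervention arm, and by-arm safety reporting is not limited to occasions both arms share

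*Combined protocol and SAP*

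**What the plan says.** **Shared occasions.** Section 4.4.3 schedules maternal weight on a "calibrated beam balance scale at the Baseline visit, and at 24-28 week, and 35-37 weeks prenatal visits". Section 4.4.1 adds: "The Usual Care group will attend the baseline and all data collection visits". Sections 4.2 and 4.7.5 have these measurements made by staff blinded to group. Each woman in either arm thus has two scheduled prenatal study weights after baseline.

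**Intervention arm only.** Table 1 gives this arm three prenatal individual visits, coaching calls and self-reported weekly weights. Section 4.5.2 states: "Weight will be coach-monitored at each intervention visit to provide ongoing surveillance". Section 4.4.1 states: "Careful monitoring for safety and prevention of weight loss during pregnancy will occur via weekly contacts". The coaching call outline asks for current weight and change since the last call, dietitians check the online accounts for unusual weight changes, and Section 4.5.1 sends this group a weekly check-in message. Table 1 gives Usual Care no individual visits, no coaching calls and no required self-monitoring.

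**Alerts and reporting.** Section 4.6 begins "The following findings would generate a safety alert and specific action if noted during any study visit". For maternal weight loss it says "Alert values will be weight loss of 4% or greater of enrollment weight for women who were overweight at enrollment", with 6% for obese women. Section 5.3 says: "Only outcome variables primarily assessed for safety reasons will be reported by treatment group, including inadequate weight gain for mother and infant". The same section puts all adverse events reported to date before a DSMB that is unmasked unless it asks otherwise.

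**The concern.** Section 4.6.1 names weight loss in pregnancy as a possible consequence of limiting calories, with fetal growth restriction as a possible result. It is therefore a harm the DSMB would want to compare between arms. A woman who is weighed or asked more often has more chances to cross a threshold or mention an injury. If findings from intervention contacts enter the by-arm counts, equal true risk looks like an excess in the intervention arm, and a real excess cannot be separated from extra looking.

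The same applies to adverse events that come to light only when the participant mentions them. Musculoskeletal injury needing medical attention is the clearest case in Section 4.6.2. The one elicitation tool described for both arms, the hospitalization form, would not capture an injury treated without admission. The adverse event definition is also tied to study participation, which adds a judgement about relatedness.

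**Working it through.** **1. The plan's own figures.** The only design calculation is for the primary outcome: SD 15 lb, difference 5 lb, 80% power, two-sided 5%. The normal approximation gives n = 2 × (1.960 + 0.842)² × (15/5)² ≈ 141.3, so 142 per group. The t-test gives 142.2, so 143, as stated in Section 5.2. This supplies the arm size (150 randomized per arm) and the SD. The plan gives no expected alert or adverse event rate, so every size below rests on assumptions.

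**2. Scheduled prenatal weighings after baseline.**
- Usual Care: 2 (24-28 and 35-37 weeks).
- Intervention, if only Table 3 visits count: 2.
- Intervention, if individual visits also count: 2 + 3 = 5.

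Usual Care has no scheduled study weight between randomization and 24-28 weeks, so a transient early loss would be seen mainly in the intervention arm.

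**3. Threshold model, same true risk in both arms.** Let q be the chance that one weighing is at alert level. With independent weighings, P(at least one alert in k) = 1 − (1 − q)^k. At q = 2% this is 1 − 0.98² = 4.0% for k = 2 and 1 − 0.98⁵ = 9.6% for k = 5, a ratio of about 2.4. Weighings on one woman are correlated, which lowers the ratio. Simulation with an equicorrelated normal threshold model (1,000,000 draws) gives these ratios for 5 versus 2 weighings:

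| Assumed q | corr. 0 | corr. 0.5 | corr. 0.8 | corr. 0.95 |
|---|---|---|---|---|
| 1% | 2.47 | 2.15 | 1.73 | 1.36 |
| 2% | 2.41 | 2.05 | 1.66 | 1.32 |
| 5% | 2.32 | 1.89 | 1.55 | 1.27 |

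At q = 2% and correlation 0.8, 3.2% of Usual Care and 5.3% of intervention women have at least one alert: about 5 versus 8 women per 150. A two-sided 5% test at 150 per arm would declare a difference in about 14% of such trials. No such test is planned; the figure only shows how misleading the counts could be.

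**4. Trajectory model, as a second check.** Weight change is a woman-specific slope plus a weekly random walk plus 3 lb of noise, scaled to the stated SD of 15 lb at 36 weeks. Assumed inputs are a mean gain of 10-20 lb, an overweight woman of 170 lb (alert at 0.04 × 170 = 6.8 lb lost) and an obese woman of 210 lb (0.06 × 210 = 12.6 lb lost). The 5 versus 2 ratio runs from 1.07 to 1.95. For an overweight woman with mean gain 15 lb and variation split evenly between slope and wandering, the chances are 10.5% and 15.9%, a ratio of 15.9/10.5 = 1.51.

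**5. Shared weights only.** With two weighings in each arm, the ratio under equal risk is 1.0.

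**6. Adverse events.** The documents give nothing from which to size the effect on participant-reported events. Only its direction can be argued.

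**The case against.** The best counter-argument is that no bias follows if a study visit means a data collection visit. The protocol mostly uses the term that way: in the blood pressure rule of Section 4.6, the third-trimester weight rule of Section 5.4.3, the data forms of Section 6.1 and the 12-month infant visit. Coaching encounters usually have other names. Weekly contacts also have their own trigger, a change of one pound or more in a week, which is separate from the alert. The one by-arm item Section 5.3 names, inadequate gain, can be derived from blinded shared weights. The DSMB can allow for unequal contact.

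Much of this stands, and it is why the effect is stated as possible. It does not close the point. The term is undefined. The rule that a repeat weight be taken at the same location as the alert weight fits alerts arising in more than one place, whereas every post-randomization prenatal visit in Table 3 is at one clinic. Nothing in Section 5.3 limits counts to shared visits or asks for their source, so the DSMB could not tell how a finding arose. Coordinator contact covers both arms (Section 4.5), but its described content is scheduling and reminders.

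The sizes above count single readings. Requiring the repeat weight within two weeks still to be at alert level lowers the ratio in the trajectory example from about 1.5 to about 1.27; requiring the same or greater loss gives about 1.45.

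A reader might also infer 11 weighings by adding the six prenatal group sessions. No passage says women are weighed there, so no figure for 11 is relied on.

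**Conclusion.** Looking is unequal by design, and the plan does not keep the unequal part out of by-arm safety counts. Maternal weight-loss alerts (on a reading the text permits) and participant-reported adverse events are open to more frequent detection in the intervention arm. For alerts, the apparent ratio with no true difference is about 1.1 to 2.5 if individual-visit weights count, across both models and their assumed rates, correlations and weight courses. It is 1.0 if only Table 3 visits count. For adverse events the size is unknown.

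Two stronger readings are not supported. A reader might conclude that the trial's key safety comparison is biased. The documents define no key safety comparison, plan no test of one, and do not list weight-loss alerts as an adverse event or as a by-arm outcome. A reader might also extend the point to adverse events as a whole. Serious adverse events count regardless of relation to the study, birth outcomes come from clinical records, the hospitalization form is used in both arms, and blood pressure and BDI-II alerts arise at shared visits. These are ascertained alike and are not affected.

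**What to change.** Leave the clinical alert process as it is for every woman. For reporting:

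- Define a study visit in Section 4.6.
- In Section 5.3 and the safety tables, base the by-arm comparison of maternal weight loss and inadequate gain on the blinded 24-28 and 35-37 week weights. Prenatal chart weights could be added if abstracted on the same schedule in both arms.
- Ask about adverse events with the same scripted question at the Table 3 visits in both arms.
- Add a source code (Table 3 visit, chart or intervention contact) to the alert and adverse event forms.
- List findings from intervention contacts separately, labelled as not comparable between arms.

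The cost is one form field, one scripted question and revised table definitions; no new visits are needed. The downside is fewer events in the comparative table, and two shared weights will miss some transient early loss in both arms. Every event is still listed and acted on.

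Separately, Section 4.6.1 applies a different trigger to "Patients who loose in excess of 5% of their weight at the Baseline visit", without the distinction by weight class in Section 4.6. The two passages must be reconciled before weight-loss counts are tabulated; no view is taken here on which is right.

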**Table 1. Description of the Interventions**

Usual Care		Intervention
Diet	Web-based access and printed pamphlet on the ChooseMyPlate.gov/ Dietary Guidelines 2010	Calorie-controlled, individually tailored DASH diet for pregnancy and lactation.

	recommendations for pregnancy/lactation; other relevant pregnancy websites and access to password protected MOMFIT website	Breastfeeding encouraged preferably exclusively for 4-6 months, with gradual introduction of “Baby-DASH” –type diet
Physical Activity	US Dietary Guidelines Website includes activity recommendations	ACOG recommendations: ≥30 minutes of moderate-intensity activity 5-7x/week; we will emphasize walking and gradually increase
Self-Monitoring	None required	Daily diet & activity ; weekly self-reported weights via LoseIt! Website/App
Group Sessions	Invited to groups (2 prenatal; 2 postpartum) covering infant CPR, care for newborns and transitions to motherhood offered by the hospital	7 group sessions: 6 prenatal; 1 postpartum
Individual Visits	None provided	5 Individual Visits conducted by study nutritionists (3 prenatal; 2 postpartum) to individualize calorie/dietary/physical activity goals, encourage breast feeding
Phone Coaching	None provided	Weekly for the first 6 weeks of intervention; monthly or more frequently as needed through 11 months postpartum
Electronic Contact	MOMFIT Website access: this group will have access to PDFs on childcare related topics that will be drawn from publicly available source No additional emails, phone or electronic contacts	MOMFIT Website Weekly emails/texts regarding electronic self-monitoring of diet/ weight/ physical activity plus an online privatized social support system for 24 months  Educational modules (PDFs) emailed 7x prenatally; 8 x post-partum

**Intervention Descriptions.** As indicated above, the Web-based (Enhanced Usual Care Group will be provided with minimal intervention as listed in Table 1.

Lifestyle Change Group (Diet Intervention Group): Nutritional Quality/Calorie Goals. Energy needs in pregnancy and breastfeeding are based on the following Institute of Medicine formula for normal weight adult females:

$$\text{Energy needs (calories)} = 354 - (6.91 \times \text{age [y]}) + \text{PA} \times (9.36 \times \text{weight [kg]} + 726 \times \text{height [m]}) + \text{addition for pregnancy/breastfeeding [3]}$$

Where PA is the physical activity coefficient:

- 1) PA = 1.00 if PAL is ≤ 30 min/day
- 2) PA = 1.14 if PAL is 30 to 60 min/day

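### After a weight-loss alert, a woman whose repeat loss is smaller but still at alert level falls under neither reassessment rule, so her prenatal provider need not be told.

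*Combined protocol and SAP*

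**What the plan says.** Section 4.6, item 1, defines the alert by BMI class. The rule for the overweight group reads: "Alert values will be weight loss of 4% or greater of enrollment weight for women who were overweight at enrollment". Obese participants have a higher threshold, 6%. At a first alert, staff tell the woman, counsel her on energy balance and weight, and adapt the intervention where appropriate. The provider is not among those actions. She returns for a repeat weight within two weeks, and two rules then apply:

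- Provider contact, with possible further changes to the intervention: "If the weight loss is the same or greater upon reassessment".
- Return to normal activity: "If the weight upon reassessment is no longer at alert values, the participant will continue current study activity".

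Section 4.6.1 has a separate rule: "Patients who loose in excess of 5% of their weight at the Baseline visit will have their diet reassessed to reassure adequate caloric intake". It names no provider. On the reason for caution, the same section says: "The effects of weight loss in this population are unknown, but could increase the risk of fetal growth restrictions".

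For the intervention arm, Section 4.4.1 adds: "Careful monitoring for safety and prevention of weight loss during pregnancy will occur via weekly contacts". For Usual Care, the electronic-contact entry in Table 1 reads: "No additional emails, phone or electronic contacts".

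**The concern.** The two reassessment rules look like a complementary pair but use different yardsticks. The first measures the repeat loss against the loss at the first alert. The second measures it against the 4% or 6% threshold. A woman who has regained a little but is still in the alert range cannot be cleared under the second rule, and the first does not require anyone to call her provider.

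This step is the only place where the protocol requires the prenatal provider to hear about weight loss. The diet deliberately limits energy intake, and the protocol itself links weight loss to possible fetal growth restriction. A hole here is therefore a safety matter. It has no bearing on power, type I error or the primary comparison.

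**Working it through.** No stated figure needs reproducing; this is a check of whether the two rules cover every case.

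**Notation.** T is the alert threshold (4% overweight, 6% obese; Section 4.6). L1 is the loss at the first alert, so L1 ≥ T. L2 is the loss at the repeat weight. Enrollment weight is taken as the Baseline visit weight.

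- Provider contact: L2 ≥ L1.
- Continue: L2 < T.
- Neither: T ≤ L2 < L1.

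The first two never overlap, because L1 ≥ T. The third is non-empty whenever L1 > T. Enumerating losses in steps of 0.1 percentage points (L1 from T to 10%, L2 from 0 to 12%) leaves 1,830 of 7,381 pairs without an action for overweight women and 820 of 4,961 for obese women, with no pair in both rules. These are counts of grid cells, not probabilities.

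**Overweight, 75 kg at enrollment (illustrative).**
- Alert: 75 × 0.96 = 72.0 kg or below.
- Diet review under Section 4.6.1: below 75 × 0.95 = 71.25 kg.
- First weight 71.4 kg: 3.6/75 = 4.8%. Repeat weight 71.7 kg: 3.3/75 = 4.4%.
- 4.4% is below 4.8% (no provider contact) and at least 4% (not cleared). Neither weight exceeds 5%, so no diet review.
- The band missed by the diet review runs from 71.25 to 72.0 kg, a width of 0.75 kg.

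**Obese, 95 kg at enrollment (illustrative).**
- Alert: 95 × 0.94 = 89.3 kg or below.
- First weight 87.4 kg: 7.6/95 = 8.0%. Repeat weight 88.4 kg: 6.6/95 = 6.9%.
- 6.9% is below 8.0% and at least 6%, so neither rule applies. The diet is reviewed because the loss exceeds 5%, but no provider contact is required.

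**Ordering of risk.** Two obese women: one at 6.0% on both occasions triggers contact because L2 = L1; one at 10% and then 9% does not, although her remaining loss is half as large again (9/6 = 1.5).

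**Do other provisions require contact?**

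| Provision | What it requires | Provider told? |
|---|---|---|
| First-alert actions (4.6) | Counselling; intervention changed if appropriate | No |
| Loss above 5% (4.6.1) | Diet review | No |
| Weekly change of 1 pound or more (4.4.1) | Review with the mother | No |
| Dietitian checks of online accounts (4.4.1) | Report to the study coach | No |
| Coordinator contact, both arms (4.5) | Scheduling and reminders | No |
| DSMB reports (5.3) | Inadequate weight gain by group, periodically | No |

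Scheduled study weights do not fill the gap quickly. Table 3 places them at 24–28 and 35–37 weeks. With an alert at 24–28 weeks and a repeat two weeks later (26–30 weeks), the next scheduled weight is 35 − 30 = 5 to 37 − 26 = 11 weeks away.

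**The case against.** The strongest reply is that the two sentences were meant as a pair, still at alert or no longer at alert, and that the first echoes the phrasing of the alert definition. That may well be the intent, but it is not what the sentence says. It compares the loss at reassessment with what came before, and the next sentence names alert values as a separate standard. If the intent was complementary, the correction only states it.

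Second, the woman affected is improving and has already been counselled, in whichever arm she is. This is true and narrows the harm: an overweight woman at 4–5% has had diet-related counselling at the first alert, even though nothing further is required at the repeat. She nevertheless remains at a value the protocol itself treats as an alert.

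Third, in the 75 kg example the two weights differ by only 0.3 kg, and since no tolerance is given, staff might fairly call the loss unchanged and make the call. That weakens this example but not the finding: the obese example differs by 1.0 kg, and 10% then 9% at 95 kg differs by 0.95 kg.

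Fourth, maternity providers weigh these women themselves (Section 5.4.3 relies on such weights), staff are free to call, and the Manual of Operations listed in the timetable may say more. These points make real harm less likely. None of them makes contact a requirement in the protocol.

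Finally, Section 4.6.1 ties the risk to limiting intake and weight gain, to which Usual Care women are not assigned. That is fair as to cause, but the alert in Section 4.6 applies to both arms.

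**Conclusion.** The concern holds. As written, any repeat loss from the alert threshold up to, but not including, the first loss has no prescribed action, and the prenatal provider need not be told. For obese women the whole gap lies above 5%, so the diet review still applies and what is missing is provider contact. For overweight women with both losses between 4% and 5%, the repeat weight triggers neither provider contact nor diet review. Intervention women also have weekly contacts; Usual Care women do not.

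The conclusion rests on the plain reading of the two sentences and on treating enrollment weight as the Baseline weight. The body weights are illustrative. The frequency is unknown, since the documents give neither an expected number of alerts nor the variability of weight over two weeks. The statistical analysis is unaffected. The wording should be corrected because a fetal-safety rule currently gives the wrong result for some women with larger remaining losses.

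**What to change.** In Section 4.6, item 1, change the condition for provider contact to: *If the weight is still at alert values upon reassessment*. Contact then applies when L2 ≥ T and continuation when L2 < T, so the two rules are exact complements and every woman who triggers contact now would do so unless she has left the alert range, which cannot occur when L2 ≥ L1 ≥ T.

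Optionally, add that the same steps apply to any later alert, because the reference to a first alert can be read either as the first alert of the pregnancy or as the first weight in each episode.

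The cost is one clause and a few more calls to providers, with no new measurement. The alert values do not change. The Consortium Safety Committee has alert values in its remit (Section 7.2.2) and should see the edit; DSMB approval is needed if it is classed as a major change (Section 7.2.4).
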